1. BACKGROUND AND RATIONALE

The cornea maintains structural integrity of the eye while providing an optically clear interface through which light may be refracted. Anatomically, it may be divided into 3 layers – epithelium, stroma and endothelium. The stroma comprises multiple layers of collagen within a matrix of water and glycosaminoglycans, while the underlying endothelium regulates stromal hydration to ensure corneal clarity.

Fuchs Endothelial Dystrophy (FED) is a degenerative disease affecting the corneal endothelium, characterized clinically by guttate excrescences on the posterior corneal surface and dysfunctional corneal endothelial cells. While patients are commonly asymptomatic in their early stages, advanced FED can be associated with significant corneal edema, scarring and impairment of visual function.

Prevalence of FED in the local Chinese population has been estimated to be in the range of 8.5% for females and 4.4% for males.¹ Genetic susceptibility to FED may be explained by the presence of genetic anomalies such as the CTG18.1 repeat expansion², TCF4 single nucleotide polymorphisms³ and SLC4A11 point mutations⁴, amongst many others.

Patients with mild FED are usually managed conservatively with the application of topical hypertonic saline eyedrops. For patients with advanced FED, endothelial keratoplasty may often be necessary. In 2014, FED represented the most common indication for endothelial keratoplasty in the United States, accounting for 47.7% (13,817 cases) of all endothelial keratoplasty procedures performed nationwide⁵. In Singapore, FED was the second most common indication for corneal transplantation.

Endothelial keratoplasty is associated with endothelial cell attrition in the range of 29.7%⁶ – 47% by the 3rd post-operative year. Additionally, the global demand for corneal graft material currently still far outstrips supply,^{7,8} critically limiting the number of patients who can potentially benefit from these surgical interventions. As such, there is a need explore alternative, sustainable strategies for the management of FED.

In 2009, Shah et al. reported the treatment of a 34 years old patient, with the combined pathologies of FED and Posterior Polymorphous Corneal Dystrophy (PPMD), by primary stripping of the central 4-5mm of Descemet's membrane without corneal graft transplantation ('Primary Descemetorhexis').⁹ Contrary to conventional expectations, there was complete repopulation of the posterior corneal surface by corneal endothelial cells following the surgery, with best-corrected-visual-acuity (BCVA) of 6/7.5 achieved by the 6th post-operative month. In 2014, Moloney et al. published a similar report of a 54 years old patient, diagnosed with FED, successfully treated by Primary Descemetorhexis.¹⁰ Rapid endothelial recovery, as evidenced by a central endothelial cell count of 620 cells/mm² and BCVA of 6/6, was achieved by approximately 6 weeks after the surgery. The success of these cases raised the prospect of Primary Descemetorhexis as a feasible alternative for the treatment of FED.

However, these anecdotal accounts must be balanced by a significant number of other

seemingly contradictory reports. For example, in 2013, Bleyen et al. reported in a prospective clinical trial of 8 patients who underwent primary descemetorhexis for the treatment of FED, that 7 of them eventually required rescue endothelial keratoplasty (DM transplant with Endothelial cells) in view of poor vision secondary to corneal edema.¹¹ FED patients treated by primary descemetorhexis (central 6 – 6.5mm) without endothelial graft were also reported by Arbelaez et al. to be dissatisfied with their visual outcomes secondary to reasons such as slow visual recovery and visual disturbances secondary to persistent stromal edema and scarring¹².

To gain a better understanding of the factors which may affect endothelial recovery following Primary Descemetorhexis, we performed an ex vivo human corneal endothelial cell culture experiment in which Primary Descemetorhexis was performed on cadaveric human cornea buttons, followed by ex vivo culture for a duration of 2 weeks to allow for endothelial recovery. A less invasive approach of denuding endothelial cells from the Descemet's membrane (DM), while maintaining anatomical integrity of the DM, was also assessed. We found that advanced patient age and the absence of DM were significantly associated with slower endothelial recovery.¹³

2. HYPOTHESIS AND OBJECTIVES

Hypothesis

Stripping of Descemet's membrane, followed by transplantation of a donor Descemet's membrane graft (i.e. 'DM transplant'), is an effective alternative to endothelial keratoplasty for the treatment of Fuchs' Endothelial Dystrophy.

Specific objectives

1. Primary aim: To evaluate the speed and extent of endothelial recovery and visual rehabilitation following DM transplant for the treatment of FED
2. Secondary aim 1: To evaluate the long term stability of post-operative outcomes of DM transplant, in terms of both endothelial cell count and best-corrected-visual-acuity, for the treatment of FED
3. Secondary aim 2: To evaluate the effect of Rho kinase inhibitor on the speed and extent of endothelial recovery and visual rehabilitation following DM transplant for the treatment of FED in patients above the age of 65. .

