3. EXPECTED RISKS AND BENEFITS

Reported complications rates in Endothelial Keratoplasty are low. DM is expected to be associated with comparable complication rates. Complications may occur either intra-operatively or post-operatively¹:

Intra-operative complications:

- Incomplete stripping of host Descemet's Membrane (DM): 1.6%
- Air bubble-related problem: 1.3%
- Scoring and stripping of host DM not possible: 0.9%
- Reverse-unfolding of donor DM: 0.5%
- Inadvertent expulsion of donor button from anterior chamber: 0.2%

Post-operative complications:

- Donor graft dislocation: 4.9%
- Air-bubbled induced pupillary block glaucoma: 2.8%

- Secondary glaucoma: 1.6%
- Partial donor graft detachment: 0.7%
- Delayed visual rehabilitation from primary failure 5%
- Blood in graft interface: 0.5%
- Bacterial endophthalmitis: 0.2%

Benefits:

- Endothelial keratoplasty is currently the standard of care for the management of advanced Fuchs' Endothelial Dystrophy
- The patient may benefit since the endothelial recovery will be from their own cells and not donor cell, hence there will no risk of rejection
- Since the cell will be from the patients own, the long term endothelial cell attrition seen in current endothelial keratoplasty techniques will not occur
- Since the cells will be from the patients own there will be no need to use prolonged topical immunosuppression and hence avoid the risk of steroid related complications e.g. glaucoma
- The patient's participation will contribute to the medical knowledge about the use of DM transplant for the treatment of Fuchs' Endothelial Dystrophy.

Risks

- The endothelial recovery may be prolonged – if this occurs then the patient will be given the option to undergo a conventional endothelial keratoplasty

References

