4.3. Inclusion Criteria

1. Fuchs' Endothelial Dystrophy (FED) as defined by any of the following criteria:
 - a. FED of at least Grade 4 on the Krachmer grading scale (i.e. greater than 5mm of confluent central corneal guttata)
 - b. Best-corrected-visual-acuity of less than 6/12 in a patient clinically diagnosed with FED of any grade, in which poor visual acuity cannot be accounted by any other significant ophthalmic disease (e.g. cataracts, age-related macular degeneration, glaucoma, optic neuropathies)
2. Patients in the range of <85 years old will be recruited for this study
3. Only individuals with the mental capacity to provide informed consent will be included.
4. Patients who are willing and able to sign a written Informed Consent Form prior to any study-specific procedures will be included
5. Patients who are willing and able to return for scheduled follow-up examinations for up to 12 months after the surgery will be included

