All DM transplant procedures will be performed at the Singapore National Eye Centre (SNEC) by a fully qualified corneal surgeon (A/[name] [name], Head of the corneal service) who regularly performs and teaches endothelial keratoplasty. The surgical procedure will involve 1) Corneal incision, 2) Stripping of the central 5-6mm diameter of host diseased Descemet's membrane and endothelium, 3) Insertion of donor Descemet's roll, 4) Unscrolling of Descemet's membrane graft and positioning onto the posterior corneal surface by an expansile gas bubble (20% Sulphur Hexafluoride, SF₆), 5) Creation of an inferior peripheral iridotomy, and 6) Closure of corneal incision with 10-0 nylon sutures.

Post-operative Care

All patients will be prescribed topical antibiotics and steroidal eyedrops post-operatively. For patients above the age of 65, an additional Rho kinase inhibitor eyedrop will be prescribed to the patient. They will be reviewed by the surgeon (A/[name] [name]) immediately after the procedure, at post-operative day 1, week 1, week 3, week 6, week 12, week 24 and week 48. Additional visits may be scheduled as required.

Primary outcomes

Measurements of best-corrected-visual-acuity, central endothelial cell count and corneal pachymetry will be obtained every month, starting from post-operative month 1. These measurements will be made by certified ophthalmic imaging technicians and Singapore Nursing Board registered staff nurses employed by the Singapore National Eye Centre.

Other outcome Measurements

1. Slit lamp examination every visit to visualize graft position and corneal hydration status
2. Intraocular measurement with Goldmann applanation tonometry every visit
3. Anterior segment optical coherence tomography (ASOCT): Non-invasive non-contact measurement with Optical Coherence Topography, Visante (day 0, day 1, week 1, month 1 and month 12)
4. Pentacam scan: Non-invasive non-contact scan with OCULUS Pentacam (day 0, month 3 and month 12)
5. Documentation of any postoperative complications including but not limited to wound leak, graft dislocation, partial graft detachment, SF₆-bubble induced pupillary block glaucoma, iris damage and bacterial endophthalmitis

All measurements will be made by the principal investigator (A/[name] [name]), certified ophthalmic imaging technicians and Singapore Nursing Board registered staff nurses employed by the Singapore National Eye Centre.

Rescue Endothelial Keratoplasty

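### Secondary aim 1 promises long-term stability, but no visit after month 12 is defined and recovery takes up part of that year, while section 3 already states that long-term cell attrition will not happen

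*Combined protocol and SAP*

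**What the plan says.** Section 2 gives secondary aim 1 as "To evaluate the long term stability of post-operative outcomes of DM transplant, in terms of both endothelial cell count and best-corrected-visual-acuity". It names no horizon. The primary aim in the same section is "To evaluate the speed and extent of endothelial recovery and visual rehabilitation following DM transplant for the treatment of FED", which rests on the same two variables.

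On the length of follow-up:
- Section 4.3 requires patients to be "willing and able to return for scheduled follow-up examinations for up to 12 months after the surgery".
- Section 5, Post-operative Care, lists reviews "at post-operative day 1, week 1, week 3, week 6, week 12, week 24 and week 48", and allows extra visits as required.
- Section 5, Primary outcomes, has acuity, central cell count and pachymetry measured monthly from month 1, with no end month.
- Section 5, Other outcome Measurements, places anterior segment OCT and Pentacam scans at month 12.

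On attrition, section 1 gives a range for conventional endothelial keratoplasty of 29.7% to "47% by the 3rd post-operative year". Section 3 lists among the benefits that "the long term endothelial cell attrition seen in current endothelial keratoplasty techniques will not occur", on the ground that the cells are the patient's own. Section 1 also says that "Fuchs Endothelial Dystrophy (FED) is a degenerative disease affecting the corneal endothelium" and describes genetic susceptibility. Section 8.1 says that no clinical efficacy data on the procedure have been published.

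Section 8.2 names the software, monthly safety analyses and three interim looks tied to 3-month follow-up. It does not define stability, a reference time point for it, or an analysis of it.

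**The concern.** Three things do not fit together. First, the aim speaks of the long term, but observation stops at about one year. Second, part of that year is not a stability period. The host's central endothelium is stripped and the donor cells are wiped off, so the central count must rise before it can be stable. Until an eye has recovered, its series is a rising curve that can mask later loss. Third, section 3 answers in advance the question that secondary aim 1 leaves open. The repopulating cells come from a patient with a degenerative endothelial disease, so the cells being the patient's own does not by itself rule out attrition or recurrence.

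What is at stake is the conclusion the trial may draw. A flat or rising central count at the last visit describes the first year. Under an aim worded as long-term stability, it could be read as support for an advantage over keratoplasty that was not observed.

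**Working it through.** The sample size of 20 is a stated restriction with no alpha, power, effect size or SD behind it, so there is no figure of the plan's to reproduce. The check concerns time.

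**1. Time line.** Week 48 is 48 × 7 / 30.4375 = 11.04 months. Against the 36-month benchmark that is 11.04 / 36 = 31%, or 12 / 36 = 33% if a month-12 visit takes place.

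**2. Window left after recovery.** Section 1 cites two successful stripping-only cases, one recovered at about 6 weeks (1.38 months) and one reaching its acuity by month 6.
- Recovery at week 6: 11.04 − 1.38 = 9.7 months to week 48.
- Recovery at month 6: 11.04 − 6 = 5.0 months to week 48, or 6 months to month 12.

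**3. Benchmark loss in that window.** Assume a constant proportional rate: λ = −ln(1 − L) / 36 per month, and loss over t months = 1 − exp(−λt).
- L = 0.297: λ = 0.00979. L = 0.47: λ = 0.01764.

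| Window | t (months) | Loss at L = 29.7% | Loss at L = 47% |
|---|---|---|---|
| Week 6 to week 48 | 9.66 | 9.0% | 15.7% |
| Month 6 to week 48 | 5.04 | 4.8% | 8.5% |
| Month 6 to month 12 | 6 | 5.7% | 10.0% |
| Month 6 to month 36 | 30 | 25.4% | 41.1% |

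**4. Could such a loss be told from no loss?** The documents give no SD for within-eye percentage change, so a range is assumed. The test is a one-sample, two-sided 5% t test (noncentral t with noncentrality d√n / SD). The 95% interval half-width is t(n−1) × SD / √n; for n = 20 and SD 10 this is 2.093 × 10 / √20 = 4.7 points. Each power cell gives the lower / upper benchmark.

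| Eyes | SD (points) | Half-width | Power, month 6 to week 48 (4.8 / 8.5) | Power, week 6 to week 48 (9.0 / 15.7) |
|---|---|---|---|---|
| 20 | 10 | 4.7 | 53% / 95% | 97% / 100% |
| 20 | 15 | 7.0 | 27% / 67% | 72% / 99% |
| 20 | 20 | 9.4 | 17% / 44% | 48% / 91% |
| 20 | 30 | 14.0 | 10% / 23% | 25% / 60% |
| 10 | 10 | 7.2 | 27% / 67% | 72% / 99% |
| 10 | 20 | 14.3 | 10% / 23% | 25% / 60% |

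The week-6 column is optimistic, because it takes every eye as recovered by week 6 and none as rescued. Ten eyes corresponds to the planned older group alone, or to what might remain after rescue surgery.

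**The case against.** This is an uncontrolled, exploratory first-in-man study of 20 patients. No objective compares attrition with keratoplasty or names year 3. Beside 3-month interim looks, calling 12 months long term is partly a matter of labels. The monthly series already allows a within-eye assessment after recovery, and section 5 requires patients to be told that the approach is experimental. All of this stands. It excuses low power, but it does not reconcile an open-ended aim with a one-year schedule, or justify a categorical benefit statement.

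A reader might go further in four ways that the documents do not support:
- That section 3 makes a 3-year claim. It says long term and gives no year; the year-3 figure is background in section 1.
- That the results would look the same whether attrition were nil or equal to keratoplasty. That depends on the SD, the window and the number of evaluable eyes, and the power above runs from 10% to nearly 100%.
- That the plan measures stability as change from baseline or month 1. No section specifies this, or any other reference.
- That consent covers only 12 months. Section 4.3 is a criterion of willingness to return, and the consent pages were not available for this review.

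It is also tempting to turn the late-window percentages into cells using the count of 620 cells/mm² in section 1. That count belongs to the 6-week case and does not carry over to the month-6 window, which comes from another patient.

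**Conclusion.** The concern holds as a mismatch between aim, follow-up and stated benefit. The defined follow-up reaches about a third of the only benchmark horizon in the protocol, and about 5 to 10 months of it can show stability, depending on when an eye recovers. The trial can describe short-term stability after recovery. It cannot establish long-term stability, and neither existing human data nor these data support stating as fact that long-term attrition is absent.

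The time line follows from the documents. The loss figures rest on a constant rate and on carrying a keratoplasty percentage over to a repopulated centre. The documents give neither the shape nor the baseline of the keratoplasty loss. If that loss is front-loaded, the benchmark loss in the late window would be smaller and harder to detect. The power figures rest on assumed SDs. They show that the answer is open and do not prove that the trial is uninformative. The point should be acted on, but it does not threaten the primary aim.

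**What to change.** 1. Reword secondary aim 1 as stability of endothelial cell count and best-corrected acuity from recovery to 12 months.
2. Assess it within eye, from a prespecified post-recovery value in the monthly series (for example month 6) to the last visit. Report the number of eyes contributing and a confidence interval.
3. State that no conclusion on long-term attrition, or on attrition relative to the year-3 keratoplasty figures, will be drawn from these data.
4. In section 3, replace the categorical statement with wording that long-term attrition or disease recurrence after the procedure is unknown.
5. Reconcile the week-48 last review, the month-12 scans and the monthly measurements without an end month, so that the last value for the stability analysis is defined.

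The cost is protocol wording and one prespecified reference time point. No additional visits are needed beyond settling which of the existing end points applies. The downside is a narrower aim and a less favourable benefit statement.

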4. STUDY POPULATION

4.1. Number and nature of subjects to be enrolled.

Patients will be recruited at Singapore National Eye Centre. The study will be a prospective, open label clinical trial where **20 patients** will be selected to undergo DM transplant for the treatment of Fuchs' Endothelial Dystrophy (FED).

The patient population for this study is patients with FED. Our previous ex vivo study has shown that older patients (>65 years old) are less likely to respond favourably to DM transplant alone and data from reported clinical cases of DM stripping alone have shown that endothelial recovery was only achievable in 50% of the cases over the age of 65 years old. Hence, an age range of <65 years old is set for this study. To include age range >65 to 85 as well, Rho kinase inhibitor eye drops will be prescribed to patients with age higher than 65 years old. 10 patients age between 65 to 85 will be recruited for DM transplant coupled with Rho kinase inhibitor. No racial, minority or gender exclusion criteria will be applied.

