5. STUDY DESIGN AND PROCEDURES/METHODOLOGY

Study Design

This is prospective, open non-randomized clinical trial. Eligible patients who fit our recruitment criteria and who are interested in surgery for improvement of symptoms related to FED will be informed of the availability of this study at the Singapore National Eye Centre. They will first be counselled on the procedures involved in conventional endothelial keratoplasty, which is the current standard of care, together with a discussion on the risks and benefits associated with endothelial keratoplasty. They will subsequently be presented with the alternative option of DM transplant, with a full explanation detailing the experimental nature of this approach, together with a discussion on the potential risks and benefits of DM transplant vis-à-vis conventional endothelial keratoplasty. They will also be counselled regarding the possibility of subsequently undergoing a rescue endothelial keratoplasty procedure in the post-operative period, should there be evidence suggesting that there is prolonged visual recovery following DM transplantation. Patients will be informed of the potential risks and benefits of the rescue endothelial keratoplasty. After provisional consent, patients will be screened for inclusion and exclusion criteria (listed above). Patients that meet the eligibility criteria will be consented and assigned to undergo DM transplant in the eye that has the more severely affected by FED. We aim to recruit a total of **20** patients for this study.

Graft Preparation

Donor corneas will be supplied by the Singapore Eye Bank. A 5-6mm Descemet's membrane graft will be prepared from the corneal button. Endothelial cells will be removed by simple wiping with a spear and removal of endothelial cells will be confirmed by trypan blue staining. All preparation will be performed by the principal investigator (A/[name] [name]), with the assistance of accredited technicians at the Singapore Eye Bank.

Surgical Procedure

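### Secondary aim 2 asks for the effect of the Rho kinase inhibitor in patients above 65, but all of them are prescribed it and no comparison is planned

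*Combined protocol and SAP*

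**What the plan says.** Section 2 gives Secondary aim 2 as "To evaluate the effect of Rho kinase inhibitor on the speed and extent of endothelial recovery and visual rehabilitation following DM transplant" for FED in patients above the age of 65.

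The inhibitor is assigned by age. Section 4.1 states "To include age range >65 to 85 as well, Rho kinase inhibitor eye drops will be prescribed to patients with age higher than 65" years, and then "10 patients age between 65 to 85 will be recruited for DM transplant coupled with Rho kinase inhibitor". Section 5 (Post-operative Care) repeats the rule: "For patients above the age of 65, an additional Rho kinase inhibitor eyedrop will be prescribed to the patient". No inhibitor is named for younger patients.

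On design, section 5 states "This is prospective, open non-randomized clinical trial", with every eligible patient assigned to DM transplant. It adds "We aim to recruit a total of" 20 patients, and section 8.1 gives the same total.

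Section 8.2 names the software, monthly safety analyses and the timing of interim analyses. It names no comparator, model, test or contrast for this aim.

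**The concern.** The effect of a drug in a population is the difference between outcomes with it and outcomes without it in that population. The aim names patients above 65, and the plan gives all of them the drug, so the without-drug side is missing. Nothing in section 8.2 supplies it from elsewhere.

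A good result in the older cohort could therefore be credited to the inhibitor when the graft alone produced it. A poor result could be held against the inhibitor when age explains it. In a first-in-man study, a reading of either kind could carry over into later work on the drug.

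**Working it through.** **Step 1. Look for a contrast inside the aim's population.** Planned patients above 65 with the inhibitor: 10 (section 4.1). Planned patients above 65 without it: 0 (sections 4.1 and 5). Section 4.1 recruits ages 65 to 85 to the inhibitor group but prescribes the drops above 65, so a patient aged exactly 65 is ambiguous; this does not change the count.

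**Step 2. Try the younger patients as controls.** The raw older-minus-younger difference is drug effect plus age effect. An observed difference of 0 fits drug 0 and age 0, drug +20 and age −20, or drug +40 and age −40 percentage points. A zero age effect cannot be presumed: section 4.1 says "older patients (>65 years old) are less likely to respond favourably to DM transplant alone", and section 1 reports slower ex vivo recovery with advanced age.

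**Step 3. Try adjusting for age.** The drug indicator switches at 65, so a regression on drug and age can be fitted. It relies on outcomes being continuous in age at 65 and on a chosen functional form. To see its precision, assume 10 younger and 10 older patients within the 20, evenly spaced ages, and residual SD = 1. With mean ages m0 (younger) and m1 (older) and within-group sums of squares S0 and S1:

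- Common slope: variance of the drug term = 2/10 + (m1 − m0)²/(S0 + S1), 17 df.
- Separate slopes, effect at 65: 2/10 + (65 − m0)²/S0 + (m1 − 65)²/S1, 16 df.
- Separate slopes, effect at the older cohort's mean age: 2/10 + (m1 − m0)²/S0, 16 df.

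Ten evenly spaced ages with spacing d have sum of squares 82.5d². For ages 55–64 and 66–75, d = 1, S0 = S1 = 82.5, m0 = 59.5 and m1 = 70.5. The common-slope variance is 0.2 + 121/165 = 0.933, so the SE is 0.966 and the half-width 2.11 × 0.966 = 2.04. At the older mean age the variance is 0.2 + 121/82.5 = 1.667, so the SE is 1.291 and the half-width 2.12 × 1.291 = 2.74.

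| Ages (younger / older) | SE, common slope | 95% half-width | SE at 65, separate slopes | 95% half-width | SE at older mean age | 95% half-width |
|---|---|---|---|---|---|---|
| 30–64 / 66–85 | 0.852 | 1.80 | 0.880 | 1.87 | 0.943 | 2.00 |
| 45–64 / 66–85 | 0.894 | 1.89 | 0.894 | 1.90 | 1.183 | 2.51 |
| 50–64 / 66–80 | 0.917 | 1.94 | 0.917 | 1.94 | 1.218 | 2.58 |
| 55–64 / 66–75 | 0.966 | 2.04 | 0.966 | 2.05 | 1.291 | 2.74 |

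A quadratic in age gives half-widths of 1.90 to 2.05 at 65. The effect at 65 detectable with 80% power (two-sided 5%) is 2.53 to 2.88 SD across the common-slope and separate-slope models. The last two columns also require extrapolating the younger patients' age trend past 65.

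**Step 4. Try the external figure.** Section 4.1 says "data from reported clinical cases of DM stripping alone have shown that endothelial recovery was only achievable in 50% of the cases" over age 65. That is stripping without a graft, so a comparison with it mixes graft and drug effects. Section 8.1 says no clinical efficacy data on DM transplant have been published, so the documents contain no graft-without-drug benchmark for older patients. Even taken at face value, 50% is a weak yardstick for n = 10. Eight recoveries of 10 give an exact 95% interval of 44% to 97%. A rule of at least 9 of 10 has one-sided alpha 0.011, and power of 15%, 38% or 74% if the true rate is 70%, 80% or 90% (assumed rates).

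**The case against.** The best defence is that this is an exploratory first-in-man study. No test, enrolment decision or safety rule depends on Secondary aim 2. All three aims use the verb evaluate, and the first two are descriptive. Section 4.1 brings in the inhibitor as a way of including older patients, so a clinical reader could take the aim to mean seeing how they do with the drops. The exploratory label does excuse low power and does limit the consequence to interpretation. It does not excuse an aim worded as the effect of a drug when the design has no contrast for it. The primary aim concerns recovery after the procedure, whereas this aim names the inhibitor's own effect.

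It can also be said that the regression figures concern a model nobody planned. They rest on assumed ages and on a 10 + 10 split that the protocol never states, and they use one outcome per patient. Baseline adjustment or the monthly repeated measurements could shrink the residual SD, and the documents give no SD for converting to clinical units. All of this is fair. The figures are an illustration; the finding that comes straight from the documents is 0 of 10 untreated, with drug and age tied together. More patients under the same rule would narrow the intervals but leave the dependence on the age model. If the 10 older patients were additional to the 20, there would still be no untreated patient above 65.

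**Conclusion.** The concern holds. The aim names a drug effect in patients above 65, and the plan contains no patient above 65 without the drug and no comparison that could stand in for one. The two substitutes in the documents fail: the younger patients because drug use follows age, the 50% figure because it comes from a different procedure. This conclusion needs no numerical assumption.

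The precision figures in the check do rest on the assumed split and age ranges, and show only that age adjustment is no practical way out. The aim should be fixed, but the effect is confined to how the older cohort's result is worded and read. The descriptive value of that cohort is untouched.

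**What to change.** Section 2: restate Secondary aim 2 along these lines: *To describe how quickly and how fully the endothelium and vision recover after DM transplant combined with Rho kinase inhibitor in the older cohort (planned n = 10). The separate effect of the inhibitor cannot be reliably estimated in this study.*

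Section 8.2: add two sentences. First, best-corrected visual acuity, central endothelial cell count and pachymetry are reported by cohort (graft alone; graft plus inhibitor) alongside any all-patient summary. Second, the older-versus-younger difference is not interpreted as an effect of the inhibitor.

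Section 4.1, as a clarification only: confirm that the 10 older patients fall within the total of 20, as sections 5 and 8.1 imply.

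The cost is a few sentences, with no extra patients or procedures and no change to treatment. One secondary aim becomes descriptive. Cohort means are less precise than the all-patient mean: the 95% half-width is 2.262/√10 = 0.72 SD with n = 10, against 2.093/√20 = 0.47 SD with n = 20. The all-patient summary can therefore stay.

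Keeping the causal aim would need a different and much larger study. Assuming 50% recovery without the inhibitor, 80% power at two-sided 5% needs 93, 39 or 20 patients per arm for 70%, 80% or 90% recovery with it (normal approximation). Splitting the planned 10 as 5 against 5 would give exact Fisher power of about 4%, 7% or 12%.
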